The Data Protection Official, Innlandet Hospital Trust, has approved applications. The collected data from the sampled patients will be de-identified and stored on a secured research server at Innlandet Hospital Trust. Participants with the capacity to provide consent will be asked to give their written consent; assessment of such capacity will be performed by the local project nurses (RN) who have experience of doing such assessment. In addition, these RN will be given extra training by the research team, who has long clinical experience in performing capacity assessment. For patients considered to lack the capacity to consent, the next of kin will be informed about the research and asked to provide consent on the patient's behalf. The consent implies an understanding of what it means to participate in the RCT and the interviews and the ability to express an informed choice. Separate consents for participating in the RCT and the interviews will be obtained. It is very unlikely that a participant would be harmed because of participating in either the RCT or the interviews. In the RCT, no new experimental treatments for the patients will be introduced, and care and treatment actions will rely on recommended national care and treatment guidelines. The patients in the control group will receive care and treatment as usual but will probably also profit of the extra attention given by the services because of participating in an RCT. It is not possible to achieve blinding of the local home cares services for the recruitment process since it is the local home care services with the aforementioned local project nurses who will be responsible for the recruitment process based on the inclusion criteria (e.g., perceived by the home care service as being in an unstable situation). This will also be the case for the results of the allocation process (i.e., to the intervention or control group).

For RQ3, both patients and their next of kin who are invited to participate in interviews will be asked to give their written consent. During the interview, the participants will be well taken care of by interviewers who have long clinical experience in working with people with cognitive impairment. If during the interview the patient indicates or signals that he/she wants to stop, the researcher will immediately end the interview. A patient who lacks understanding of what it means to participate in research but consents to participate in an interview will be given the opportunity to bring their next of kin to the interview. Even if some of the participants have cognitive impairment and lack of capacity to understand the concept of research, they may still have the capacity to understand and express relevant views on the services they receive. Hearing their experiences with crises and how it was handled by the service is therefore important. This is a patient group that is prone to crises, but also to neglect and probably poorer treatment from the service since they often have difficulty promoting their needs, preferences, and desires. This is an important reason why this group of patients should be included in both the RCT and the interview study with the common final aim to improve approaches towards crises.

Since the local project groups can consist of staff members from home care services, precautions will be taken to ensure that the members of the local project group that inform the users and their next of kin, don't have any care-relation to the participants invited to participate in the interview study (RQ3). In this way the users of home care services and their next of kin should do not feel obliged to participate upon being informed about the project. Members of the local project groups will only share information about the project with users and hand out written information and consent forms. In this way, the members of the local project group will not know whether the users of home care services and their next of kin have consented to participate or not.

Potential impact of the proposed research

Due to the patients' multimorbidity, changes in home care services can hardly be introduced as standardized solutions based on single diagnoses but should be made through holistic approaches based on multimorbidity and functional impairments. The PRACTIC study will enhance innovation where health professionals, management, and users actively participate in the development of new knowledge and a new approach towards each patient and where this process is adapted to local structural conditions. The project is likely to enforce a systematic cooperation with the GPs, where diagnostic work-up and follow-up become one of the most important tasks. For the home care services, this means a cultural change from a mainly task-oriented service based on failure in activities of daily life, to an interdisciplinary assessment and follow-up service of functional impairment in the user group. If successful, the intervention can, based on the process evaluation study in WP3, easily be implemented in the healthcare services with minimal extra resources. Improving the approaches to crisis may reduce the use of specialist healthcare services.

Project organization and collaboration

This study is a part of the PRACTIC study: Preventing and approaching crises for frail community-dwelling patients through innovative care. The project is owned by the Research Centre for Age-Related Functional Decline and Disease (AFS), Innlandet Hospital Trust, Ottestad, Norway. The project manager of the PRACTIC study is PhD MD [name], research leader at AFS, who will, together with professor [name] (AFS), PhD MD [name] (AFS) and PhD RN [name] (AFS) also be part of the research team in this project. The research group has extensive research experience in health care services for patients with complex care needs.

The project has organized two reference groups, one with end-users (patients and next of kin) and one with staff from the home care services including GPs. The reference groups will meet with the central project group regularly during the project period. A steering group will be organized, consisting among others of stakeholders from municipalities and the county governor of Innlandet. The design of the project will enable close cooperation with end-users and stakeholders in the municipalities, through the establishment of local project groups in each municipality.

Collaborators in the project

Collaborating municipalities will recruit participants to the different sub-studies, **organize local project groups**, be active in the local adaptation and development of the TIME model, and participate in the reference groups. So far, **four municipalities have signed an intentional agreement**. The municipalities will contribute to the teaching of staff and data collection.

Hochschule für Gesundheit (hsg) Bochum, University of Applied Sciences (Germany, [name]), has developed the case conference model WELCOME-IdA, similar to the TIME model, and published papers on a step-wedged **cRCT and the process evaluation** (61-63). They will contribute to the plan for the analyses, interpretation of the results, and writing of papers in WP2 and WP3. The Norwegian National Advisory Unit on Ageing and Health (Norway, [name]), has extensive experience in performing research in municipality healthcare in Norway, including recruitment of participants from home care service. They will participate in all WPs, in the design of the study, recruitment of municipalities and participants, analysis and writing of papers. The Centre for Development of Institutional and Home care Services (USHT) Innlandet (PhD [name] and [name]) has a **network of collaborating municipalities** in Innlandet county, and a network of USHTs in Norway. They will contribute to the design of the study, will **recruit 30 municipalities** for the study, and will contribute to the organisation of the study and collaboration with the municipalities. Collaborating partners in the study will not have access to any of the data.

Plan for activities

Three papers will be published in international peer reviews open journals. In addition, results from this study will be presented by oral presentation at national and international congress.

Time schedule

PhD 75% position for four years

01.06.22: Application to the Regional Committees for Medical and Health Research Ethics.

Application to the The Data Protection Commissioner, Innlandet Hospital Trust.

01.04.22 – 31.08.22: : Detailed planning of the project, recruitment of municipalities, signing agreements with municipalities and establishing local project groups in each municipalities.

01.09.22 – 31.12.22: Educational sessions for the local project nurses in the home-care services designated to assist with the inclusion of patients and their next of kin.

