Study protocol

Project title:

Preventing and approaching crises for frail community-dwelling patients through innovative care (PRACTIC) - an effectiveness study

Participatory action research in a cluster randomised controlled trial

This protocol represents **Work Package 2 (WP2)** in the PRACTIC-study (**Preventing and approaching crises for frail community-dwelling patients through innovative care**). The PRACTIC-study consist of four work packages:

WP1	Characteristics of crises in frail patients receiving home-care services
WP2	Evaluation of the effect of an adapted version of the TIME model in the prevention and treatment of crises in frail community-dwelling people
WP3	Pre-specified process-evaluation of the intervention in the RCT
WP4	Administration and project coordination

Abstract

Background:

Demographic changes, with an increasing number and proportion of older people with multimorbidity and frailty, will put more pressure on home care services in municipalities as well as on specialist health care. Frail multimorbid people receiving home care services are at risk of developing crisis often resulting in adverse events, coercive measures, and acute institutionalisation. Crises also pose increased demands and stress on the next of kin. There is a lack of evidence based interventions to prevent and resolve crises in community settings. Our hypothesis is that through interventions targeting the patients, the next of kin, the patients' social context, and healthcare service, crises may be prevented and resolved. This project aims to test the effectiveness of an adapted version of a bio-psychosocial person centred model the Targeted Interdisciplinary Model for Evaluation and Treatment of Neuropsychiatric Symptoms, (TIME) to prevent and resolve crises for frail community-dwelling people receiving home care services. In addition, we will analyse factors associated with the effect of TIME, and we will explore the experiences the users have with the introduction of TIME in the services.

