People who are at an increased risk of developing crises are often frail. Crises are major stressors for patients, their next of kin, and the care staff and often lead to adverse events, acute institutionalisation and the use of coercion (15, 16). Crises can be described as '*a process in which the stressors cause an imbalance requiring an immediate decision which leads to a desired outcome and therefore crisis resolution*' (15). In the Preventing and approaching crises for frail community-dwelling patients through innovative care (PRACTIC) study, we will operationalize this definition to describe crises in practice as "critical challenges and symptoms that demand immediate and new actions". The challenges and symptoms that trigger and maintain crises are heterogeneous and vary between patients and may include depression, poor nutrition status, rejection of care, incontinence, neuropsychiatric symptoms (NPSs), and social isolation (12). The 'Mind the Gap report' from the Advisory Board of the Global Forum for Health Care Innovators states that 1–5% of community-dwelling patients are high-risk patients and 15–35% are patients with an increasing risk. The literature on crises among patients receiving home care services has mainly explored the phenomenon in relation to people with dementia living at home (15, 16).

The need for new multicomponent interventions possible to adapt to the local context

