For RQ3 we will use an explorative design with qualitative in-depth interviews of dyads with 15 patients and next of kin who participated in the RCT. Qualitative methods provide contextual based knowledge about people's experiences and how they interpret, understand and link meaning to events (40). The aim is to get a deeper understanding of how crises were approached during the trial as experienced by the users of the home care services in the intervention municipalities. Because the questions and topics of the interviews concern personal critical situations, individual interviews are perceived as the most appropriate method of collecting data.

Settings and target population

This study is part of the larger PRACTIC (Preventing and approaching crises for frail community-dwelling patients through innovative care) study. The trial will include approximately 30 randomly selected municipalities and their home care services from all health care regions in Norway. From each region, a sample of small, medium, and large municipalities will be invited to participate. From those 30 included municipalities, 150 users of home care services and their next of kin will be invited to participate in the trial. The local project team will collaborate with the research team in the adaption of TIME to the local context during the trial. Specially trained nurses (see below, section: Control and intervention phases of the study) will support the research team in the recruitment of participants and the data collection. However, the care providers for the intervention will be the regular staff in the home care services.

Inclusion criteria for patients are: (1) in need of home care services, (2) a score ≥ 5 on the Clinical Frailty Scale (indicating mild to severe frailty) (41), and (3) perceived by the home care service as being in an unstable situation with a high risk for acute institutionalisation or showing resistance to care. The only exclusion criterion is an expected short life expectancy (i.e., < 4 weeks).

Inclusion criteria for next of kin (for RQ3) are (1) being next of kin of a user of home care services who meets the above mentioned inclusion criteria (2) regular contact with the patient (i.e., at least once a week).

Fig.1. The PRACTIC trial: Flowchart of the clusters and individuals throughout the phases of the trial

RQ1 and RQ2 Sample size calculation based on the primary outcome

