The proposed sample of 150 participants is based on a power calculation with clusters of approximately five participants from each of the 30 municipalities. Based on a previous trial, a minimal clinically important average difference on the PGSI scale is set to 2 points between intervention and control group with a standard deviation (SD) for change of 2.83 in each group (40). To observe a statistically significant difference with a power of 80%, an intra-cluster (municipality) correlation coefficient (ICC) of 10% and an estimated attrition rate of 25% for the primary outcome at three months, we will need approximately 150 participants. We assume a high attrition rate since the participants are at high risk for acute institutionalisation (see inclusion criteria).

This trial must perform cluster randomisation, with the municipality as the cluster, for two main reasons. The intervention is a biopsychosocial intervention that involves the entire interdisciplinary team and staff in the home care services of the participating municipalities to optimize the approach towards a group of patients in the municipalities. In addition, without cluster randomisation, the study runs the risk of transmitting all or parts of the intervention model to the individual control patients in the same municipalities (42). The patients in the control group will receive care and treatment as usual, but they will probably also profit from the extra attention given by the home care services because of their participation in the RCT and because of the use of the measure for the primary outcome, the PGSI. In this way, we can isolate any effects on goal achievements to prevent or resolve crises to the main difference between IMs and CMs, i.e., the TIME intervention.

RQ3 Selection of participants for the individual in-depth interviews

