Specially trained nurses (data assessors) from the project's research centre who are not affiliated with the municipalities will, together with staff members in the home care services, assess patients' baseline characteristics before randomisation. These data assessors will after randomisation be blinded to the randomisation result. They will assess the effect of the intervention via telephone by interviewing the participants, the next of kin and the staff members who know the patient best, at three months and six months after baseline assessments. All assessors are nurses with substantial experience and formal training on the use of the assessment scales. They will attend a one-day course on the use of the assessments scales before start of the trial. A description of the questionnaires, including data assessors, respondents and the time point(s) at which they are administered, is provided in Table 1.

Baseline data and primary and secondary outcome measures

The primary outcome of the trial is the difference in the change between the intervention and control groups in individual goal achievement to resolve or alleviate the challenges regarding crises between baseline and three months using the PGSI (scale of 1–10) (34). We chose this primary outcome because there is a need for a targeted outcome that comprises the variability in a heterogeneous population. It is very unlikely that a participant would be harmed due to participation in the RCT; therefore, it is not deemed necessary to have a harm outcome in the study. In the RCT, no new experimental treatments for the patients will be introduced, and care and all treatment actions will rely on recommended national care and treatment guidelines.

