The secondary outcomes are the differences in the change between the intervention and control groups in the PGSI scale at 6 months, in neuropsychiatric symptoms (NPSs) measured by the Neuropsychiatric Inventory (NPI-NH) (45), quality of life measured by the Quality of Life in Late-Stage Dementia scale (QUALID) (46, 47), distress perceived by the next of kin measured by the Relative Stress Scale (48), rejection of care measured by the Minimum Data Set (49), activities of daily living assessed with the Physical Self-Maintenance Scale (PSMS) (50), prescribed medications collected from the medical records (51), frailty measured with the Clinical Frailty Scale (CFS) (52), institutionalization at three and six months, and pain and discomfort assessed by the EQ-5D questionnaire (53) at six months. All these questionnaires have been proven to have acceptable validity and reliability. The trial will also collect data to be used as covariates in the RCT and to describe the sample of participants. These data will be collected with questionnaires answered by the staff in home care services:

- a) Age (covariate in the RCT), sex, level of education and employment status, marital status, living conditions (living alone or with someone)
- b) Hours a week and type of home care service
- c) Relation to next of kin (e.g., next of kin and how often they meet)
- d) Physical health measured with the General Medical Health Rating Scale (GMHR) (54)
- e) Cognitive function assessed by the Clinical Dementia Rating Scale (CDR) (55) (covariate in the RCT).

Table 3 Overview of the data collection in WP2 with primary and secondary outcome measures

Data collected	Interviewers	Respondents	Baseline	3 months	6 months
Characteristics of the participants					
Age ^a , gender, level of education and employment status, marital status and living conditions	Data assessors from AFS ^b	Staff members in the home care services	X		
Hours a week and type of service from the home care service	Data assessors from AFS	Staff members in the home care services	X		
Number of visits per day from the home care service	Data assessors from AFS	Staff members in the home care services	X		
Relation to next of kin (e.g., next of kin and how often they meet)	Data assessors from AFS	Staff members in the home care services	X		
Diseases (known diagnosis)	Data assessors from AFS	Staff members in the home care services	X		

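### The protocol decides against any harm outcome on grounds that do not cover events in unstable patients, and plans no record of deaths or acute hospital admissions by arm

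*Protocol*

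**What the plan says.** The protocol's section on baseline data and outcome measures gives two reasons and a conclusion. The first reason is "It is very unlikely that a participant would be harmed due to participation in the RCT". The second is that "no new experimental treatments for the patients will be introduced, and care and all treatment actions will rely on recommended national care and treatment guidelines". From these it concludes that "it is not deemed necessary to have a harm outcome in the study". The section on ethical considerations repeats both reasons.

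Participants are "perceived by the home care service as being in an unstable situation with a high risk for acute institutionalisation or showing resistance to care". They must score at least 5 on the Clinical Frailty Scale, and the only exclusion is an expected survival of under four weeks. The section defining crisis says that crises "often lead to adverse events, acute institutionalisation and the use of coercion", and the abstract says much the same.

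The secondary outcomes include "institutionalization at three and six months, and pain and discomfort assessed by the EQ-5D questionnaire (53) at six months". They also include NPI-NH, QUALID, the Relative Stress Scale, rejection of care, PSMS, medication and the Clinical Frailty Scale. Table 3 has no row for institutionalisation, and none for death or hospital admission.

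**The concern.** The stated reasons concern harm caused by being in the trial and the absence of new treatments. The trial, however, compares two ways of handling crises in people already at high risk. The intervention changes what is assessed, who meets about the patient and which actions follow. Guideline-based care in both arms does not show that serious events will be equally frequent in both; the randomised comparison would show that, provided the events are recorded.

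Two readings of the results are at stake. First, fewer institutional placements in one arm could reflect resolved crises, deaths before placement, or a shift to hospital. The protocol itself expects, in its section on potential impact, that better crisis handling may reduce use of specialist care, yet hospital admission is not a listed outcome. Second, the primary comparison is made at three months with substantial attrition expected. If deaths are not recorded by arm, death cannot be told apart from other loss when that comparison is read.

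**Working it through.** **Which events are planned for collection.** The outcome text, Table 3 and the data-collection procedures were compared with the events that matter here.

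| Event | Planned? |
|---|---|
| Institutionalisation | Yes, in the outcome text at three and six months; not in Table 3; not defined |
| Worsening of symptoms, function, quality of life or carer stress | Partly: NPI-NH, PSMS, QUALID and Relative Stress Scale at baseline, three and six months; EQ-5D pain and discomfort at baseline and six months |
| Death | No |
| Acute hospital admission as such | No |
| Use of coercion | No; rejection of care describes the patient's behaviour, not what the service does |

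**How precise a comparison by arm would be.** The protocol gives no figure on harms, so there is nothing of its own to reproduce. The inputs are:

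- 150 participants ("we will need approximately 150 participants") in 30 municipalities. The RQ3 section refers to 15 intervention municipalities, so 15 × 5 = 75 per arm.
- ICC 0.10, the only one in the protocol. It was set for the primary outcome and is borrowed here.
- Event rates of 5%, 10% and 20%. These are assumptions, because the protocol gives none. They imply about 4, 7.5 and 15 events per arm.

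Design effect: 1 + (5 − 1) × 0.10 = 1.4.

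Half-width of the 95% interval: 1.96 × √[2 × p × (1 − p) / 75 × 1.4].

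- p = 0.05: 1.96 × √(0.095/75 × 1.4) = 1.96 × 0.0421 = 0.083
- p = 0.10: 1.96 × √(0.18/75 × 1.4) = 1.96 × 0.0580 = 0.114
- p = 0.20: 1.96 × √(0.32/75 × 1.4) = 1.96 × 0.0773 = 0.151

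If 25% are lost, 56.25 per arm and 3.75 per cluster remain, and the design effect is 1 + 2.75 × 0.10 = 1.275. At p = 0.10: 1.96 × √(0.18/56.25 × 1.275) = 1.96 × 0.0639 = 0.125.

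The result depends little on the ICC. At p = 0.10 with 75 per arm, an ICC of 0.05 (design effect 1.2) gives 1.96 × √(0.18/75 × 1.2) = 0.105.

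**What could be detected by a test.** At 75 per arm and a design effect of 1.275 to 1.4, 80% power (two-sided 5% assumed) from control risks of 5%, 10% and 20% would need intervention-arm risks of about 23–24%, 31–32% and 44–45%. A formal test of harm is out of reach, and the purpose can only be descriptive.

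**The case against.** The strongest reply is that the protocol considered the question and gave a reason. It adds assessment, case conferences and evaluated actions to ordinary care, so serious harm caused by the trial is improbable. It also has outcomes that would show deterioration: institutionalisation and the scales listed above. And no planned estimate or test is wrong because of this decision.

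Much of this stands, and it limits the point. A reader might infer any of the following, and the protocol does not support them:

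- *That the protocol contradicts itself.* The abstract and the definition of crisis describe what crises lead to. The harm statement concerns the effects of taking part. Both can be true.
- *That the trial aims to keep unstable patients at home.* The stated aim is to prevent and resolve crises, and the primary outcome is goal achievement. The preference for living at home is background.
- *That the results would be uninterpretable for safety.* The scales and institutionalisation give partial evidence.
- *That deaths would go unreported.* The protocol commits to CONSORT recommendations and a participant flowchart, whose content is not visible here, so deaths may appear among the reasons for loss.

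What does not stand is the step from improbable harm through participation to no need for a harm outcome. The scales do not record death or hospital admission, and they are most likely to be missing when such an event has occurred. Institutionalisation is undefined. Even if it were meant to include hospital stays, it would merge them with nursing-home placement.

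Coercion is a weaker case. The protocol does not define it, and it would be reported by staff who know the allocation.

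**Conclusion.** The point holds as a weak design choice that is cheap to improve. The protocol takes an explicit decision, so this is not a detail left to an analysis plan, and the reasons given do not cover deaths and acute hospital admissions in this population. As planned, a difference in goal achievement or institutionalisation could not be set beside those events by arm.

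The gain from recording them is modest. With the borrowed ICC and assumed event rates, intervals of roughly ±8 to ±15 points would neither establish safety nor rule out a moderate excess. They would show a large imbalance and help explain who is missing at three months. Nothing in the protocol suggests that the intervention is harmful, and this point does not claim so.

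**What to change.** In the section on outcome measures, replace the statement that no harm outcome is needed, and align the matching text under ethical considerations. At the three- and six-month telephone interviews, which blinded assessors already hold, record death with its date, and acute hospital admission separately from nursing-home institutionalisation. Add these items and institutionalisation to Table 3, with respondent and time points. Report counts and proportions by arm with cluster-adjusted 95% intervals, descriptively and without hypothesis tests. Add coercion only if a definition is fixed first, and note that the staff reporting it are not blinded.

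The cost is a few extra items in calls already planned and one descriptive table with wide intervals. Sample size, power and the primary analysis do not change. One caution on timing: the time schedule ends follow-up on 31.12.23. If the calls are already complete, these items would have to be collected afterwards, and the protocol does not say whether its approvals would allow that.
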